#### 3.6.3 Nasal Endoscopy Assessments

Ethmoid cavities will be assessed by endoscopy during Screening, on Day 1 prior to LYR-220 administration/sham procedure, and at Week 4, 12, 24 (before LYR-220/sham removal), and 25/Follow Up visits.

Local safety evaluation of ethmoid cavity will be performed on Day 1 prior to LYR-220 administration/Sham procedure and at Week 4, 12, 24, and 25/Follow Up visits to document presence of epistaxis, mucosal injury, and any other adverse local observations in ethmoid cavity.

The severity of epistaxis will be determined by the Investigator on the basis of his or her clinical judgment and the following definitions:

- Mild: blood-tinged mucus, nonactive nose bleeding
- Moderate: active nose bleeding that does not require medical intervention
- Severe: frank nose bleeding that requires medical intervention

The severity of mucosal injury will be determined by the Investigator because of his or her clinical judgment and the following definitions:

- Mild: evidence of epithelial erosion
- Moderate: evidence of ulceration through the epithelial layer with exposed underneath tissue

Severe: perforation

Counts and percentages of subjects will be presented at baseline for the following:

- Severity of Epistaxis (Left): [MILD | MODERATE | SEVERE | NA]
- Severity of Epistaxis (Right): [MILD | MODERATE | SEVERE | NA]
- Severity of Mucosal injury (Left): [MILD | MODERATE | SEVERE | NA]
- Severity of Mucosal injury (Right): [MILD | MODERATE | SEVERE | NA]

Newly identified or worsened endoscopic findings will be presented at each scheduled visit and in overall.

# 3.6.4 Vital Signs

Vital sign measurements will include blood pressure (systolic and diastolic, mm Hg), and pulse rate (beats per minute), aural/oral temperature (°C or °F), and respiration rate (breaths per minute). All measurements will be obtained after the subject has been seated for at least 5 minutes.

Vital signs will be measured at the Screening visit. Descriptive statistics for values will be presented.

#### 3.6.5 Ophthalmologic Assessments

The ophthalmologic assessment of IOP and slit-lamp examination to identify development or worsening of cataract will be conducted at Screening and Week 25/Follow Up visits. The cataract assessment will be conducted according to the Simplified Cataract Grading System authored by the World Health Organization (WHO) Cataract Grading Group. Subject's eyes will be dilated with mydriatics following the WHO guidance for cataract assessment. IOP may be measured using Goldmann applanation tonometer, noncontact tonometer, or tono-pen; however, it is recommended that the same method be used for consistency across serial assessments on a given subject. IOP assessment will also be performed at Week 4 and 12 visits. Assessments will be conducted by an ophthalmologist/optometrist who is blinded to the subject's treatment assignment.

The number and percentage of subjects with clinically significant increase of IOP will be presented by visit and in overall. Descriptive summary statistics on the values and change from base line of IOP will be presented by visit.

The number and percentage of subjects with newly identified or worsened cataract will be presented by visit and in overall.

# 3.6.6 Oral/Systemic Corticosteroids Rescue

Other oral steroids for rescue treatment of CRS or intravenous or oral steroids for another reason that are prescribed to the subject are to be recorded in the eCRF. All efforts should be made to complete the Week 25/Follow Up assessments including nasal endoscopy and CT before starting treatment with oral/systemic corticosteroids. However, the subject should continue with the study treatment and follow-up visits. The investigator (or designee) will record the dates and dosing information (dosage form, daily dose, duration, name of drug) on the appropriate page(s) of the eCRF. Indication for oral/systemic corticosteroid use will also be

captured. A course of oral/systemic corticosteroids is considered continuous if treatment is separated by less than 7 days.

The number and percentage of subjects with oral/systemic corticosteroids rescue will be presented by treatment group.

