8.4.2 Ethmoid Cavity Opacification Imaging

Ethmoid cavity opacification will be assessed by CT at the time points specified in the Schedule of Assessments (Section 8.1), unless medically contraindicated. The Screening CT should be performed anytime between the Screening and Day 1 visits. Alternatively, a historical CT scan can be used if done within 3 months preceding the Screening visit. The follow-up CT will be conducted within 5-9 days after the LYR-220 removal procedure at Week 25 visit. If a subject is experiencing or recovering from a cold, acute exacerbation of nasal allergy, or upper respiratory tract infection at the Week 25 visit, the CT assessment should be performed 4 weeks after resolution of the adverse event. If a subject early terminates from the study or requires SCS or sinonasal surgery as rescue treatment during the study, every attempt should be made to perform the follow-up CT before subject receives the rescue treatment. The percent opacification of ethmoid cavity will be evaluated by an imaging core lab.

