### 3.1.1 Analysis Day

Analysis day for analysis visit windows (i.e., "Aday") will be calculated from the date of study treatment (LYR-220 or sham) administration. The day of study treatment administration will be Aday 1, and the day immediately before Aday 1 will be Aday -1.

Additionally, analysis day relative to the last dose day (i.e., "Aenday") will be calculated from the date of last dose of study treatment. The day of last dose of study treatment will be Aenday 0, and the day immediately after Aenday 0 will be Aenday 1. Data collected up to 31 days after end of treatment will be included in the analysis.

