## 3.1.2 Analysis Visits

Analysis visits will be used for efficacy and safety endpoint analysis. Follow up visits are defined as any visits during 1 day and up to 31 days after end of treatment. Scheduled visits will be assigned to analysis visits as recorded on the Case Report Form (CRF) if they are within the corresponding analysis visit windows described in the tables below. Scheduled visits that do not fall in the corresponding analysis visit windows are considered unscheduled visits when assigning analysis visits. In order to maximize the data available for assessments with regular scheduled visits, where possible, results from unscheduled visits will be assigned to analysis visits according to the following visit windows. When multiple visits are within the same analysis visit window, the one closest to the target day will be used. For efficacy endpoints, if two values are equally distanced, select the value before the target day.

If both paper-based patient-reported outcomes and ePRO are completed at the same day, ePRO will be used for analysis.

If multiple ePRO are completed at the same day and the input are different, the entry having the worst total score will be used for analysis. If multiple ePRO are completed at the same day and the input are identical, the earliest entry will be used for analysis.

An unscheduled visit that does not fall under any window will remain in the database and will be included in the listings.

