# **Table 1f. Visit Windows for Ethmoid Cavity Opacification**

Analysis Visit	Target Analysis Day	Low Analysis Day	High Analysis Day
Week 25/follow-up*	Aenday 7	Aenday 0	Aenday 31

\* post-treatment follow-up.

\* post-treatment follow-up.

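### A CT taken before on-treatment systemic-steroid rescue always falls outside the SAP's CT window, and no rule says which CT counts for that subject

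*SAP*

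**What the plan says.** SAP 3.6.6 (matching protocol 8.3.6) addresses subjects who are to receive SCS: "All efforts should be made to complete the Week 25/Follow Up assessments including nasal endoscopy and CT before starting treatment with oral/systemic corticosteroids". It continues: "However, the subject should continue with the study treatment and follow-up visits". Protocol 8.4.2, repeated in SAP 3.1.4.13, treats that scan as the endpoint scan: "every attempt should be made to perform the follow-up CT before subject receives the rescue treatment".

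The analysis window is in SAP Table 1f, "Visit Windows for Ethmoid Cavity Opacification". Its only row is "Week 25/follow-up* Aenday 7 Aenday 0 Aenday 31". SAP 3.1.1 defines the clock: "The day of last dose of study treatment will be Aenday 0, and the day immediately after Aenday 0 will be Aenday 1". SAP 3.1.2 adds: "Follow up visits are defined as any visits during 1 day and up to 31 days after end of treatment". Under the same section a scheduled visit outside its window is treated as unscheduled, and: "An unscheduled visit that does not fall under any window will remain in the database and will be included in the listings".

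SAP 3.4.2.7 analyses change in opacification at Week 25/Follow-up by ANCOVA and does not mention rescue. SAP 3.1.10.3.2 leaves missing CT unimputed and refers to Section 3.4.2 for intercurrent events.

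**The concern.** The plan asks sites for a follow-up CT before SCS, and its own window then keeps that scan out of the analysis. What remains for the rescued subject is one of two things:

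- (a) a second CT at the actual Week 25 visit, taken after SCS, which is the only scan inside the window; or
- (b) no second CT, so that the subject drops out of the ANCOVA.

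Under (a) any lasting steroid effect on opacification is counted as the randomised arm's result. Under (b) subjects whose disease worsened are removed. If rescue is more common on sham, either may make sham look better and bias the difference toward no effect.

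The conversion endpoint in SAP 3.1.4.16 is exposed too. One of its two alternative criteria is a Week 25 CT clear of ethmoid disease, and only surgery disqualifies, so a CT cleared by steroids could count as conversion.

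**Working it through.** The plan gives no figure on this point to reproduce. The check is one of dates, followed by an illustration of size.

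**1. Which day is Aenday 0.** Last dose is loose wording for a single-administration implant. If it meant insertion on Day 1, a scheduled CT 5-9 days after removal on Day 169 (Days 174-178) would have Aenday 173-177, and every scheduled CT would miss Table 1f. Read as removal, the same CT has Aenday 5-9, around the target of 7. SAP 3.1.2 also counts follow-up from the end of treatment. Aenday 0 is therefore read as matrix or sham removal.

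**2. Where the pre-rescue CT falls.** Aenday of CT = Aday of CT − Aday of removal; the window is 0 to 31. The Week 24 visit is Day 169 ± 7.

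- Removal on Day 162: 0 of 160 on-treatment days (Day 2 to the day before removal) are inside.
- Removal on Day 169: 0 of 167.
- Removal on Day 176: 0 of 174.

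The latest possible value is Aenday −1. Examples with removal on Day 169: Week 4, 29 − 169 = −140; Week 10, 71 − 169 = −98; Week 12, 85 − 169 = −84; Week 20, 141 − 169 = −28.

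**3. Whether another rule brings it back.**

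- Recording the scan as Week 25 on the CRF does not help. SAP 3.1.2 honours the CRF visit only inside the window.
- The rescue estimand in SAP 3.4.2.1.1, which sets aside post-rescue values, is extended by name to cardinal symptoms, CRS-PRO and PGIS (3.4.2.2 to 3.4.2.4), not to CT. If it did cover CT it would remove outcome (a) and leave (b).
- Protocol 9.8.1.1.1 uses LOCF for post-rescue and missing data but leaves missing follow-up CT unimputed. The SAP has no LOCF rule for CT and does not say whether a scan in no analysis visit could be carried forward.

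**4. Size of outcome (a).** All inputs are assumed: SCS rescue in 20-30% of sham and 5-10% of LYR-220 subjects, and a post-SCS CT 10-20 percentage points clearer than the pre-rescue CT. With 20 per arm this is 4-6 sham and 1-2 LYR-220 subjects.

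Shift in difference = (sham rate − LYR-220 rate) × clearing.

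- Smallest: (0.20 − 0.10) × 10 = 1.0 point.
- Largest: (0.30 − 0.05) × 20 = 5.0 points.

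This supposes that every rescued subject has a second CT and that all clearing is due to the steroid, although some could be the flare settling. Protocol 2.1 says that gains from oral steroids typically last no longer than 3 months. Rescue at Week 4 comes 21 weeks before the Week 25 CT, and rescue at Week 20 only 5 weeks before, so the shift is smaller for early rescue.

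**5. Precision under outcome (b).** SE ratio when k of 20 are lost in one arm = √[(1/20 + 1/(20 − k)) / (2/20)]: k = 1, 1.013; k = 2, 1.027; k = 4, 1.061; k = 6, 1.102. The loss of precision is modest; selective loss is the larger concern.

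**The case against.** **Other text may already govern.** The protocol's LOCF sentence can be read as replacing a post-rescue CT with the pre-rescue one, and SAP Section 5 declares no change from the protocol analyses. SAP 3.1.10.3.2 can be read as bringing CT under the rescue estimand. Against this, the LOCF text sits under the symptom-score heading, and the estimand is extended endpoint by endpoint without CT. What stands is that outcome (a) is arguable, not certain. The ambiguity itself still needs resolving.

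**Using the Week 25 CT regardless of rescue is a legitimate treatment-policy choice.** That stands. But the SAP does not state that choice for CT, and it states a hypothetical strategy for the symptom scores.

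**The pre-rescue CT is not a clean substitute.** This also stands. Rescue follows worsening CRS, so the scan is taken in a flare, whereas the plan delays the Week 25 CT after colds, allergy exacerbations and respiratory infections. It is also earlier, and the matrix is in place in the LYR-220 arm only. It could make the more often rescued arm look worse. A reader might infer that the pre-rescue CT gives the unbiased answer, or that the plan requests it in order to obtain a steroid-free reading; the documents state neither.

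**The endpoint is minor.** CT is one of 11 secondary efficacy endpoints in a Phase II trial that was not sized on power, and it is not among the Primary Lock outputs. That limits the consequence but does not remove the contradiction.

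**Conclusion.** The point holds for SCS started while study treatment is ongoing. The scan that the plan calls the follow-up CT cannot enter the Week 25 analysis under Table 1f, and SAP 3.4.2.7 does not say what takes its place. The conclusion rests on reading Aenday 0 as removal, which the Week 25 target supports.

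The direction, toward no effect, depends on rescue being more common on sham. The size is unknown because the documents give neither a rescue rate nor a steroid effect on CT; 1.0 to 5.0 points is an illustration of outcome (a) only. A reader might infer that the CT result is bound to be biased against LYR-220. The documents do not support that: rescue could be rare, balanced or early.

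Not affected are surgery rescue, where treatment stops first and Aenday 0 moves to that time; SCS started after removal; and CTs taken after both matrices have dislodged. The safety primary endpoint is untouched. This should be corrected, but it does not threaten the trial's main conclusion.

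**What to change.** Before the Primary Lock unblinding, reconcile SAP Table 1f, 3.1.4.13, 3.4.2.7 and 3.6.6:

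- Assign the post-baseline CT taken before the first SCS dose to the Week 25/Follow-up analysis visit, whatever its Aenday.
- Where both scans exist, report the ANCOVA also with the as-scheduled Week 25 CT as a sensitivity analysis.
- Where no pre-rescue CT exists, state the handling; for example, keep the in-window Week 25 CT and flag it, so that the subject is not dropped. The pre-rescue scan is only a best-efforts request, so this case will arise.
- State which CT feeds the CT criterion of the conversion endpoint, and show that endpoint both ways.
- Record the rule in SAP Section 5.

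The cost is SAP wording and programming. No new scans and no change in patient management are needed. The conversion criterion is defined in the protocol by the Week 25 CT, so using another scan there is a documented departure. The report should disclose the limits of the pre-rescue CT: earlier timing, flare, and matrix present in one arm only. The sensitivity analysis shows how much they matter. SAP 4.2 treats changes after the primary lock as post hoc; if that lock has passed, label the rule accordingly.

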## 3.6.7 Sinonasal surgery (actual or planned) for CRS

For subjects who have a surgery or have a scheduled date for sinonasal surgery as rescue for CRS, the reason (worsening signs and/or symptoms during the study), the date the surgery was indicated, expected or actual surgery date, and the type and outcome of surgery will be recorded in the eCRF. Types of sinonasal surgery include, but are not limited to, repeat functional endoscopic sinus surgery, balloon sinuplasty, turbinate reduction, septoplasty or polypectomy, or any endoscopic procedure that results in sinonasal tissue removal.

If the surgery is to be performed during the study treatment period, the study treatment will be discontinued and all procedures/assessments for the Week 24 visits will be completed prior to the surgery. Additionally, all efforts should be made to complete the Week 25/Follow Up assessments including nasal endoscopy and CT prior to the surgery. The subject will be discontinued from the study.

If the surgery is scheduled after the planned end of study, the investigator (or designee) should follow-up with the subject on the occurrence and outcome of the surgery until the time of database closure for the study.

The number and percentage of subjects with sinonasal surgery will be presented by treatment group for the following:

- Full Endoscopic Sinus Surgery (FESS),
- Balloon Sinuplasty,
- Turbinate Reduction,
- Septoplasty or Polypectomy,
- Other.

#### 4 ANALYSIS TIMING

## 4.1 Interim Analysis

No interim analysis is planned.

#### 4.2 Primary Lock Analysis

A Primary Lock Analysis (PA) will be conducted to support a late-breaking presentation of high-level results from this BEACON study at the annual meeting of the American Rhinologic Society (ARS) in September 2023. The SAP will be finalized and signed prior to this analysis. Any changes to the pre-planned analyses in this SAP that affects statistical analysis after the primary lock analysis will be considered posthoc. The study team members who are involved in data cleaning for the final data base lock will not receive the detailed patient-level results from the PA.

The PA will be performed after all subjects in Part 1 and Part 2 complete Week 24 visit. After the database is locked (i.e., freeze of eCRFs), the subject's treatment allocation will be unblinded.

The analysis data sets (i.e., SDTM and ADaM) for this analysis will be locked. Selected data will be generated as listed below.

- · Disposition,
- Demographics,
- Baseline disease characteristics,
- Change from baseline (CFBL) in SNOT-22 total score at Weeks 2, 4, 6, 8, 12, 16, 20, 24 and 28,
- CFBL in the average composite score over the preceding 7 days of 3 cardinal symptoms (3CS) and individual cardinal symptom scores at Weeks 2, 4, 6, 8, 12, 16, 20, 24 and 28,
- Overview of Adverse Events.
- Treatment-Emergent Adverse Events by Preferred Term,
- Treatment-Emergent Adverse Events by System Organ Class and Preferred Term,
- Product-Related Treatment-Emergent Adverse Events by System Organ Class and Preferred Term,
- Treatment-Emergent Serious Adverse Events by System Organ Class and Preferred Term.
- Product-Related Treatment-Emergent Serious Adverse Events by System Organ Class and Preferred Term,
- Treatment-Emergent Adverse Events Leading to Discontinuation of Study Treatment by System Organ Class and Preferred Term.

# 4.3 Final Analysis

The final database lock and analysis will occur after all subjects in Part 1 and in Part 2 have completed the study (Week 28/Follow Up visit). After the database is locked, the final analysis will be generated. TFLs, SDTM data and AdaM data along with associated files will be provided. Associated files may include annotated CRFs, SDTM specifications, SDTM programs, AdaM specifications, AdaM programs, TFL programs, and CDISC Define packages for both SDTM and ADaM data. The CSR will be written based on the final TLFs.

# 5 CHANGES FROM PROTOCOL-SPECIFIED STATISTICAL ANALYSES

There is no change from the protocol-specified statistical analyses.

## 6 PROGRAMMING SPECIFICATIONS

Analyses will be performed using SAS® version 9.4 or higher. PK parameters will be calculated via SAS® and confirmed with the results of Phoenix WinNonlin™ (version 8.1 or higher). All data will be presented in subject data listings which will be sorted by subject and visit date as applicable. Detailed Programming Specifications will be provided in a separate document.

